### **Immune-Related Adverse Events**

Summaries irAEs will be based on all treated subjects and will use the pre-defined list of MedDRA high-level group terms, high-level terms and preferred terms that is current at the time of analysis. ([APPENDIX 1](#) contains the most recent version of the list, version 20.0)

The following summary tables of irAEs will be restricted to events occurring in the on-study phase (see [Section 4.3.1.1](#)).

- On-study phase irAEs (worst CTC grade [Any grade, 3-4, 5] of any event and of events by SOC)
- On-study phase irAEs (worst CTC grade [1, 2, 3, 4, 5, unknown, any grade] of any event and of events by SOC)
- On-study phase irAEs by subcategory (worst CTC grade [Any grade, 3-4, 5] by subcategories of GI, liver, skin, endocrine, neurological, other)
- On-study phase irAEs by subcategory (worst CTC grade [1, 2, 3, 4, 5, unknown, any grade] by subcategories of GI, liver, skin, endocrine, neurological, other)
- Time to onset of on-study phase grade 3-5 irAEs by subcategory (GI, liver, skin, endocrine, neurological).
- Time to resolution of on-study phase grade 3-4 irAEs by subcategory (GI, liver, skin, endocrine, neurological)
- Number of episodes of on-study phase grade 3-4 irAEs by subcategory (GI, liver, skin, endocrine, neurological)

Listings by subject will be produced for all on-study and post-study irAEs (including steroid therapy received and details of resolution).

### **Immune-Mediated Adverse Reactions**

Summaries of imARs will be based on all treated subjects.

The following summaries for on-study phase imARs will be provided (for subcategories as specified in the core imAR SAP):

- Summary of subjects with worst grade of grade 2 on-study phase imAR
- Summary of subjects with worst grade of grade 3-4 on-study phase imAR

- Summary of subjects with worst grade of grade 5 on-study phase imAR
- Summary of subjects with worst grade of grade 2-5 on-study phase imAR and outcome of hospitalization by subcategory (worst CTC grade [2+, 3-4, 5] by subcategories)
- Summary of subjects with worst grade of grade 2-5 on-study phase imAR who received blood transfusion by subcategory (worst CTC grade [2+, 3-4, 5] by subcategories)
- Time to first onset (any grade) of imARs for subjects with worst grade of grade 2-5 on-study phase imAR by subcategory
- Time to resolution of imARs for subjects with worst grade of grade 2-5 on-study phase imARs by outcome of resolution by subcategory
- Time to resolution of imARs for subjects with worst grade of grade 2-5 on-study phase imARs by use of systemic corticosteroids and outcome of resolution by subcategory
- Time to resolution of imARs for subjects with worst grade of grade 2-5 on-study phase imARs by use of high dose systemic corticosteroids and outcome of resolution by subcategory
- Time to resolution of imARs for subjects with worst grade of grade 2-5 on-study phase dermatitis imARs by use of topical corticosteroids and outcome of resolution
- imARs leading to study drug discontinuation by use of high dose systemic corticosteroids for subjects with worst grade of grade 2-5 imARs, by subcategory
- Distribution of outcome (last reported grade) of imARs for subjects with worst grade of grade 2-5 on-study phase imARs by subcategory
- Distribution of outcome (last reported grade) of imARs for subjects with worst grade of grade 2-5 on-study phase imARs by use of systemic corticosteroids by subcategory
- Distribution of outcome (last reported grade) of imARs for subjects with worst grade of grade 2-5 on-study phase imARs by use of high dose systemic corticosteroids by subcategory
- Distribution of outcome (last reported grade) of imARs for subjects with worst grade of grade 2-5 on-study phase dermatitis imARs by use of topical corticosteroids
- Distribution of outcome (last reported grade) of imARs for subjects with worst grade of grade 3-5 on-study phase imARs by subcategory
- Duration of administration of systemic corticosteroids for imARs for subjects with worst grade of grade 2-5 on-study phase imARs by subcategory
- Duration of administration of systemic corticosteroids for imARs for subjects with worst grade of grade 2-5 on-study phase imARs by high dose systemic corticosteroids, by subcategory
- Duration of administration of topical corticosteroids for imARs for subjects with worst grade of grade 2-5 on-study phase dermatitis imARs
- Distribution of immunosuppression administration for imARs for subjects with worst grade of grade 2-5 imARs by subcategory
- Distribution of administration of hormonal therapy for immune-mediated endocrinopathies for subjects with worst grade of grade 2-5 on-study phase immune-mediated endocrinopathies by use of high dose of systemic corticosteroids by subcategory
- Summary of Dosage of Systemic Corticosteroids for Subjects with Worst Grade of Grade 2-5 imARs, by subcategory

- Number of Subjects Receiving High Dose Systemic Corticosteroids for any imAR for Subjects with Worst Grade of Grade 2-5 imARs
- Cross-tabulation of imAR Grade at First Onset Versus Worst imAR Grade, by Class
- Time From First Non-Severe (Grade 1 or 2) to First Severe (Grade 3-5) Onset for imARs, by Class

**For endocrinopathies only:**

- Time on Hormonal Replacement Therapy for Endocrinopathy imARs, by type of therapy (adrenal replacement therapy [identified as systemic corticosteroids (identified by the BMS physicians) used for adrenal replacement (as indicated by the investigator on the concomitant medication CRF, use=adrenal insufficiency)], thyroid medication, testosterone medication) and by medication status (therapy discontinued, therapy ongoing)
- Distribution of Outcome (Last Reported Grade) of Endocrinopathy imARs for Subjects with Worst Grade of Grade 2-5 imARs, by Hormonal Replacement Therapy Status (adrenal replacement therapy discontinued, adrenal replacement therapy ongoing, hormonal replacement therapy other than adrenal replacement therapy, no hormonal replacement therapy)
- Serious Endocrinopathy imARs for Subjects with Worst Grade of Grade 2-5 Endocrinopathy imARs, by Hormonal Replacement Therapy Status (adrenal replacement therapy discontinued, adrenal replacement therapy ongoing, hormonal replacement therapy other than adrenal replacement therapy, no hormonal replacement therapy)
- Listing of Endocrinopathy imARs and Hormonal Replacement Therapy status for subjects with on-study endocrinopathy imARs
- Time on Systemic Corticosteroid for Endocrinopathy imARs, by medication status (therapy discontinued, therapy ongoing)

Present the table for 3 categories:

- ANY SYSTEMIC CORTICOSTEROID
- SYSTEMIC CORTICOSTEROIDS USED FOR ADRENAL REPLACEMENT
- SYSTEMIC CORTICOSTEROIDS FOR USE OTHER THAN ADRENAL REPLACEMENT

- Listing of Time on Systemic Corticosteroids for Endocrinopathy imARs, for subjects with on-study endocrinopathy imARs, by medication status (therapy discontinued, therapy ongoing)

Present the listing for 2 categories:

- SYSTEMIC CORTICOSTEROIDS USED FOR ADRENAL REPLACEMENT
- SYSTEMIC CORTICOSTEROIDS FOR USE OTHER THAN ADRENAL REPLACEMENT

- Distribution of Outcome (Last Reported Grade) of Endocrinopathy imARs by Use of Systemic Corticosteroids for Subjects with Worst Grade of Grade 2-5 Endocrinopathy imARs

Present the table for 3 categories:

- SYSTEMIC CORTICOSTEROIDS USED FOR ADRENAL REPLACEMENT

- SYSTEMIC CORTICOSTEROIDS FOR USE OTHER THAN ADRENAL REPLACEMENT
- NO SYSTEMIC CORTICOSTEROIDS
- Time to Resolution for Endocrinopathy imARs by use of Systemic Corticosteroids and by Outcome of Resolution for Subjects with Worst Grade of Grade 2-5 Endocrinopathy imARs  
Present the table for 3 categories:
  - SYSTEMIC CORTICOSTEROIDS USED FOR ADRENAL REPLACEMENT
  - SYSTEMIC CORTICOSTEROIDS FOR USE OTHER THAN ADRENAL REPLACEMENT
  - NO SYSTEMIC CORTICOSTEROIDS

**The following listings will be produced for all class imARs:**

- Listing of On-Study and Post-Study imARs
  - For events with imAR=Yes or Unknown or No, and including reasons for imAR=Yes/No
  - Post induction events at class level (i.e., events that occur for the first time after the induction period and prior to the start of the re-induction period without any events in the same class that occurred during the induction period) will be flagged.
  - Novel re-induction events will be flagged.
  - This listing will include all classes: enterocolitis, dermatitis, hepatitis, endocrinopathies, neuropathies, other.
  - Present all treatment regimens.
- Listing of Time to Onset and Resolution of on-study imAR
  - This listing will include classes: enterocolitis, dermatitis, hepatitis, endocrinopathies, and neuropathies.
  - Present only ipilimumab containing regimens.
- Listing of imARs Initiated After 90 Days of Last Dose Corresponding to on-study imARs Class
  - This listing will include classes: enterocolitis, dermatitis, hepatitis, endocrinopathies, and neuropathies.
  - Present only ipilimumab containing regimens.
- Listing of New imARs Initiated During High Dose Systemic Corticosteroid Treatment of Early Onset imARs for subjects with on-study imAR
  - This listing will include all classes: enterocolitis, dermatitis, hepatitis, endocrinopathies, neuropathies, and other.
  - Present only ipilimumab containing regimens.

The following summaries for novel re-induction imARs will be provided:

- Summary of subjects with worst grade of grade 2 imAR
- Summary of subjects with worst grade of grade 3-4 imAR
- Summary of subjects with worst grade of grade 5 imAR

## **Multiple Events Analyses**

For the multiple event analyses, the following summary tables will be provided:

- A table showing the total number and rate (exposure-adjusted) of occurrences for all on-study AEs occurring in at least 5% of the subjects treated
- A table showing the total number and rate (exposure-adjusted) of occurrences for all on-study irAEs
- A table showing the number of subjects experiencing an on-study AE once or multiple times

No formal comparisons/statistical testing will be performed. A listing will be produced that displays the unique instances of all AEs, i.e. after duplicates have been eliminated and overlapping and contiguous occurrences of the same event have been collapsed.

### ***7.6.2 Clinical Laboratory Evaluations***

Laboratory parameters will be analyzed based on all treated subjects with an on-study test conducted. For the list of laboratory parameters, see [Section 7.3.7](#).

- On-study hematology (worst CTC grade)
- Baseline vs. on-study hematology (worst CTC grade)
- On-study liver function (worst CTC grade)
- Baseline vs. on-study liver function (worst CTC grade)
- On-study renal function (worst CTC grade)
- Baseline vs. on-study renal function (worst CTC grade)
- On-study pancreatic function (worst CTC grade)
- Baseline vs. on-study pancreatic function (worst CTC grade)

### ***7.6.3 Deaths***

Deaths will be analyzed based on all treated subjects.

- All deaths (with reason)
- Deaths within 30 days of last dose received
- Deaths within 90 days of last dose received

All deaths, together with the reason, will be listed by subject; deaths occurring within 30 days following the last day of study treatment, and within 90 days following the last day of study treatment will be indicated.

### ***7.6.4 Resource Utilization***

The number of subjects hospitalized, with primary reason for hospitalization, will be tabulated, as will be type of non-protocol-specified visit. Summary statistics (N, mean with SD, median, minimum, maximum) will be provided by treatment group for number of hospitalizations per subject, length of stay, number of non-protocol-specified visits per subject.

- Summary of hospitalization

- Summary of non-protocol-specified visits

### **7.6.5      *Immunogenicity***

A listing will be provided of all available ADA assessments. The frequency of ADA positive subjects and of neutralizing ADA positive subjects will be tabulated.

### **7.7      *Pharmacokinetic Analyses***

PK parameters will be summarized and listed. PK data obtained from this study may be pooled with data from other studies to perform an integrated population PK analysis (including assessment of covariate effects on PK), as well as exposure-response analysis for selected safety and efficacy endpoints. These analyses will be described in (a) separate report(s).

### **7.8      *Health-Related Quality of Life***

At each time point for analysis, the number of subjects who completed the questionnaires will be reported as a percentage of eligible subjects. Change from baseline analyses will be based on all randomized subjects who have a baseline measurement and an on-study assessment for the time-point of interest.

#### **7.8.1      *EORTC QLQ-C30***

The following descriptive analyses will be conducted:

- EORTC QLQ-C30 questionnaire completion rate, defined as the proportion of questionnaires actually received out of the expected number (i.e., number of subjects on treatment or in follow up), will be calculated and summarized for each assessment time point by treatment group.
- Mean scores and post-baseline score changes will be summarized using descriptive statistics (N, mean with SD and 80% CI, median, first and third quartiles, minimum, maximum) for all scales at each assessment time point.
- A line graph summarizing the mean post-baseline score changes will be produced for all scales.

#### **7.8.2      *EuroQoL EQ-5D-3L***

The following descriptive analyses will be conducted:

- EQ-5D-3L questionnaire completion rate, defined as the proportion of questionnaires actually received out of the expected number (i.e. number of subjects on treatment or in follow up), will be calculated and summarized for each assessment time point by treatment group.
- A by-subject listing of the level of problems in each dimension, corresponding EQ-5D-3L health state (i.e., 5-digit vector), EQ-5D-3L utility index score, and EQ-5D-3L VAS score will be provided.
- Proportion of subjects reporting problems for the 5 EQ-5D-3L dimensions at each assessment timepoint will be summarized by level of problem and by treatment group. Percentages will be based on number subjects assessed at assessment time point.
- For the EQ-5D-3L utility index and VAS scores, separately:

- Mean score and mean change from baseline at each assessment time point will be summarized by treatment group using descriptive statistics (N, mean with SD and 80% CI, median, first and third quartiles, minimum, maximum).
- A line graph summarizing the mean post-baseline score changes will be produced

## 8 CONVENTIONS

Unless otherwise noted, the following conventions should be understood to apply. Further conventions may be detailed in the Data Presentation Plan.

The duration between two dates will be calculated as [later date] – [earlier date] + 1 day. Study day will be calculated as

$$Day = \begin{cases} [\text{assessmentdate}] - [\text{first medicationdate}], & \text{if assessment before first medication,} \\ [\text{assessmentdate}] - [\text{first medicationdate}] + 1 \text{ day,} & \text{if assessment on or after first medication} \end{cases}$$

Assessment times will be calculated relative to the first date of study medication, i.e. Day 1.

Events will be considered as occurring within X days (e.g. deaths within 30 days, deaths and AEs within 90 days) of last dose of study medication if [event date] – [last dosing date] ≤ X.

The following factors will convert days to months or years: 1 month = 30.4375 days, 1 year = 365.25 days.

### Conventions for Partial/Missing Dates

Unless specified otherwise the following conventions will be used for imputing partial dates:

- If only the day of the month is missing, the 15th of the month will be used to replace the missing day.
- If both the day and the month are missing, "July 1" will be used to replace the missing information.
- If a date is completely missing, it will be considered as missing.

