## 6 STUDY PERIODS, TREATMENT REGIMENS AND POPULATIONS FOR ANALYSES

## 6.1 Study Periods

- Baseline period:
  - Baseline evaluations or events will be defined as evaluations or events that occur before the date and time of the first dose of study treatment. Evaluations on the same date and time of the first dose of study treatment will be considered as baseline evaluations.
  - In cases where the time (onset time of event or evaluation time and dosing time) is missing or not collected, the following definitions will apply:
    - ◆ Pre-treatment AEs will be defined as AEs with an onset date prior to but not including the day of the first dose of study treatment.
    - ◆ Baseline evaluations (laboratory tests, etc.) will be defined as evaluations with a date on or prior to the day of first dose of study treatment.

If there are multiple valid assessments, the assessment that is closest to day (and time if collected) of the first dose of study treatment will be used as the baseline in the analyses. If multiple assessments are collected on the same date (and time, if collected), the assessment with the latest database entry date (and time, if collected) will be considered as baseline, unless mentioned otherwise.

- Post baseline period:
  - On-treatment AEs will be defined as AEs with an onset date and time on or after the date and time of the first dose of study treatment (or with an onset date on or after the day of first dose of study treatment if time is not collected or is missing). For subjects who are off study treatment, AEs will be included if event occurred within a safety window of 90 days after the last dose of study treatment. No ‘subtracting rule’ will be applied when an AE occurs both pre-treatment and posttreatment with the same preferred term and grade.
  - On-treatment evaluations (laboratory tests, etc.) will be defined as evaluations taken after the day (and time, if collected and not missing) of first dose of study treatment. For subjects who are off study treatment, evaluations should be within a safety window of 90 days after the last dose of study treatment.

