## 7 STATISTICAL ANALYSES

### 7.1 General Methods

No interim analyses are planned for this study. The final analysis will be performed when a minimum of 2 year follow-up is reached by all randomized subjects.

Unless otherwise noted, the bulleted titles in the following subsections describe tabulations of discrete variables, by the frequency and proportion of subjects falling into each category, grouped by treatment (with total). Percentages given in these tables will be rounded to the first decimal and, therefore, may not always sum to 100%. Percentages less than 0.1 will be indicated as ‘< 0.1’. Continuous variables will be summarized by treatment group (with total) using the mean, standard deviation, median, minimum and maximum values. Subject listings will be produced to accompany the tabulations. Time-to-event variables (e.g. time-to resolution) will be analyzed using the Kaplan-Meier technique. When specified, the median will be reported along with 80% CI using Brookmeyer and Crowley method (using log-log transformation for constructing the confidence intervals). The conventions to be used for imputing partial dates for analyses requiring dates are described in [Section 8](#).

Frequency tables of subject characteristics and subset analyses of efficacy endpoints (including those by M-substage and BRAF mutation status) will be based on the assessment recorded on the baseline CRF. However, stratified analyses will be based on the variables used by the IVRS to randomize the subject.

Assessments taken during re-induction and subsequent progression follow-up phase will not contribute to derived endpoints, such as BOR or PFS, since these assessments are necessarily following an initial progression. However exploratory version of these endpoints corresponding to the administration of re-induction therapy may be performed (if there are sufficient data) - details will be provided in the DPP.

All statistical analyses will be carried out using SAS software (SAS Institute, Cary, North Carolina, USA), unless otherwise noted.

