### **7.3.6      *Clinical Complaints and Findings***

Events with onset prior to the date of first dose will be examined (whether recorded on the pre-treatment events CRF or on the on-treatment adverse events CRF).

- Pre-treatment events (worst CTC grade of any event and of events by SOC)

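### On the visible text, SAP Section 8's default date imputation can place an AE with a partial onset date before first dose and move it out of the on-study safety tables

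*SAP*

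**What the plan says.** SAP 7.1 sends analyses that need dates to Section 8: "The conventions to be used for imputing partial dates for analyses requiring dates are described in" that section. Section 8 opens its partial-date rules with a general scope: "Unless specified otherwise the following conventions will be used for imputing partial dates". The defaults are:

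- Day missing: "If only the day of the month is missing, the 15th of the month will be used to replace the missing day".
- Day and month missing: "If both the day and the month are missing, 'July 1' will be used to replace the missing information".
- Nothing known: "If a date is completely missing, it will be considered as missing".

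Section 8 then gives separate rules for date of death, date of progression and date of last tumor assessment. An imputed death date is checked against the last known alive date. An imputed progression or tumor-assessment date is checked against a complete date of death. No rule or check for AE onset appears in the visible text.

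SAP 6.1 classifies AEs by onset date and time, and by date where time is missing or not collected: "Pre-treatment AEs will be defined as AEs with an onset date prior to but not including the day of the first dose of study treatment". SAP 7.3.6 summarizes events with onset before first dose as pre-treatment events, "whether recorded on the pre-treatment events CRF or on the on-treatment adverse events CRF". SAP 7.6.1 limits the AE, SAE and irAE summary tables to the on-study phase and refers to Section 4.3.1.1 for it. The by-subject listings in 7.6.1 cover all AEs.

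**The concern.** The default is a neutral midpoint, but the quantity derived from it is a before-or-after classification against a known date. If first dose falls in the second half of a month, the 15th of that month always precedes it. An AE recorded with only that month is then pre-treatment by construction, even though its known date parts are compatible with onset after first dose. The CRF page on which the site entered it does not protect it, because 7.3.6 overrides the page.

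At stake are counts in the on-study AE, SAE and irAE summaries. Any loss concentrates in the days soon after first dose, since only events in the first-dose month (or, for year-only dates, the first-dose year) are exposed. A fully missing onset is a separate gap: it is left missing and meets neither the pre-treatment nor the on-treatment definition in 6.1.

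**Working it through.** The SAP states no figure on this point, so there is none to reproduce.

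**Inputs.** The default rules are from SAP 8 and the classification by onset against first dose is from SAP 6.1. Assumptions: first-dose dates are spread uniformly over the calendar, true onset is uniform over the stated span, and the on-study phase follows the on-treatment definition in 6.1.

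**When it happens.** An on-treatment AE is misclassified if its imputed onset is earlier than the first-dose date.

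- Day missing: this requires onset in the first-dose month and first dose on the 16th or later (185 of 365 dates, 50.7%). Example: first dose 20 March, true onset 25 March recorded as March only. The imputed date is 15 March, so the AE is pre-treatment.
- Year only: this requires onset in the first-dose year and first dose after July 1 (183 of 365 dates, 50.1%). Example: first dose 1 September, onset 10 November. The imputed date is July 1, 62 days before first dose.

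In all other cases an on-treatment AE is not moved before first dose.

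**Share for day-missing AEs, 30-day month.** For first dose on day d, the days left in the month, counting day d, are 31 − d.

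- Misclassified: sum over d = 16 to 30 of (31 − d) = 15 + 14 + … + 1 = 120.
- All onsets 0 to 29 days after first dose: 30 × 30 = 900. Share = 120/900 = 13.3%.
- Same-month onsets only: sum over d = 1 to 30 of (31 − d) = 465. Share = 120/465 = 25.8%.

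**Same calculation with real month lengths, 365-day year.** Each month of length L contributes 1 + 2 + … + (L − 15) misclassified pairs: 136 for 31 days, 120 for 30 days, 91 for 28 days. The total is 7 × 136 + 4 × 120 + 91 = 1,523. Over onsets 0–30 days this is 1,523/(365 × 31) = 13.5%. Enumeration over other spans gives:

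| Onset after first dose | Day-missing AEs misclassified |
|---|---|
| 0–7 days | 39.2% |
| 0–14 days | 27.7% |
| 0–21 days | 19.0% |
| 0–30 days | 13.5% |
| 0–90 days | 4.6% |

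**Year-only AEs.** The same enumeration gives 46.0% over 0–30 days and 37.8% over 0–90 days.

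**Reverse error.** A day-missing event before first dose becomes on-treatment if it lies in the first-dose month and first dose is on the 1st to 15th. Each month contributes 0 + 1 + … + 14 = 105 pairs. For events in the 28 days before first dose the share is 12 × 105/(365 × 28) = 12.3%.

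Every percentage is a share of partially dated events, not of all AEs.

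**The case against.** The strongest objection is that the section controlling entry to the AE tables cannot be read here. SAP 7.6.1 refers to Section 4.3.1.1 for the on-study phase, and that section is listed in the contents but is not in the reviewed text. Section 8 also says that further conventions may be in the Data Presentation Plan. Either could hold an AE-onset rule, and Section 8's default yields to one. This stands: a reader might infer that the plan has no AE rule, but the documents show only that none is visible.

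A reader might also infer that these events vanish from safety reporting. They do not. They remain in the all-AE listings and appear in the pre-treatment summary, and deaths have their own tables.

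A third inference would be a one-sided or large loss of safety events. The documents do not support that either. Midpoint imputation errs both ways: 12.3% of day-missing events in the 28 days before first dose become on-treatment. The number of partial onset dates is not stated and could be near zero. Infusion reactions are a weak example because they arise at dosing visits with known dates, and year-only onsets are an extreme case.

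The reverse error does not cancel the problem, however. It adds events to the on-study tables, whereas the error at issue takes out events that may have followed dosing, and that is the less cautious direction for a safety summary.

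**Conclusion.** The point holds as a gap on the visible text. Read together, SAP 8, 6.1, 7.3.6 and 7.6.1 let a partially dated AE that is compatible with onset after first dose be counted as pre-treatment and left out of the on-study AE, SAE and irAE summaries. The effect is confined to day-missing AEs in the first-dose month with first dose on the 16th or later, and to year-only AEs in the first-dose year with first dose after July 1.

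About 13% of day-missing AEs starting in the first 30 days are affected, and more when onset is closer to first dose. This rests on uniform dates and on the on-study phase matching 6.1. The absolute count cannot be derived from the documents and may be small. The primary endpoint, the 2-year survival rate, does not depend on AE dates. An AE-onset rule in Section 4.3.1.1 or the Data Presentation Plan could settle the matter.

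**What to change.** First confirm whether Section 4.3.1.1 or the Data Presentation Plan has an AE-onset rule. If so, cite it in Section 8. If not, add to Section 8:

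- If the known part of the onset date matches the month (or, for year-only dates, the year) of first dose, and the AE stop date is not before first dose, impute the later of the default date and the first-dose date.
- Otherwise keep the default. In later months nothing is misclassified, and moving those onsets to the first of the month would shift time to onset and time to resolution for no gain.
- Count a fully missing onset as on-treatment unless the stop date is before first dose.
- Treat a stop date as before first dose only when its known parts show this, so that a mid-month imputed stop date does not defeat the floor.

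Applied to all 365 first-dose dates and onsets 0 to 153 days after first dose, the floor reduces on-treatment AEs classed as pre-treatment to 0 under both default rules. In the March example the imputed onset becomes the later of 15 and 20 March, which is 20 March.

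The cost is a few lines of text and one derivation. The Protocol (Section 1.2) gives a database lock of 03Jun2019, so if tables already exist, the step is to count AEs with partial onset dates and rerun the derivation. The downside is that some true pre-treatment events with the same partial date will count as on-treatment. The stop-date condition limits this, and the number should be small if partial dates are few.
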